The [name] lab has developed an oral sugars tolerance test (OSTT) to determine the magnitude of liver stimulation of lipogenesis when an individual consumes an oral bolus of sugars [1]. In the present study, we will use this protocol to determine whether 10 days of drug treatment will significantly reduce fasting and sugar-stimulated lipogenesis. The study is divided into 3 parts (described below) which will allow us to make minor adjustments in the dose of drug after the first six subjects' results are available to optimize the suppression of lipogenesis, while also minimizing any side effects the drug might have.

The overall study design is shown in **Figure 1** and the timing of the procedures is identical for all three parts of the study. The study design is a repeated-measures, with each subject serving as his own control. The study will be unblinded with respect to the research staff working directly with the subjects. However, laboratory personal who will be running the biochemical analyses will be blinded to whether they are analyzing baseline or post-treatment samples.

Summary of study objectives

This study's goal is to identify a drug dose that will effectively lower lipogenesis, while minimizing any side effects. We will start studying two subjects at a dose of 50 mg/day, and continue at 50 mg/day for the following 4 subjects, closely monitoring side effects and drug activity.. Depending on the degree of side effects, effectiveness of the dose in reducing lipogenesis, and PK activity for the initial 6 subjects, the dose for the last 6 subjects may be adjusted to a targeted dose that will provide the most significant reduction in lipogenesis with the least amount of side effects, if any. A decision tree to serve as the basis for these decisions is presented as **Supplementary Figure 1** in the Appendix

We will accomplish the following **specific aims**:

Aim 1 (Part 1, subjects 1 and 2). First, treat two subjects with 50 mg/d of drug for 10 days to preliminarily determine the effects of the drug to lower lipogenesis. Measure fasting and sugar-stimulated lipogenesis before and after treatment, while monitoring for side effects. **Hypothesis 1:** *A 10d duration of 50 mg/d treatment will lower acute lipogenesis stimulated by a bolus of sugars by at least 2% and result in no, or minimal side effects.*

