Aim 2 (Part 2, subjects 3-6): Test an additional 4 subjects according to the results of Part 1. **Hypothesis 2:** *Additional subjects treated at the same dose will refine the statistical confidence in the observations of Objective 1.*

Aim 3 (Part 3, subjects 7-12): Using the final targeted dose of drug, study 6 subjects using the same in-patient protocol as in the other aims. **Hypothesis 3:** *Using the final dosing scheme, the last six subjects will demonstrate a significant reduction in fasting and stimulated lipogenesis, with the lowest side effects, if any.*

Study Details

The sources of research materials will include following items.

Screening: Research subject and family medical history, demographic data, vitals, height, weight, BMI calculated, and screening laboratory tests including a CMP, hepatitis panel, CBC with differential, concentration of insulin, a lipid panel, apolipoproteins B and A1, ECG, and HbA1c. Demographic data (plus other related data, e.g., emergency contact person), smoking history are collected, along with lifestyle information including food/beverage/alcohol intake and physical activity will be obtained via questionnaire and a urine sample is used for a general drug screen.

Inpatient CRC studies: Blood is processed to obtain plasma and the sample used in the isolation and measurement of blood metabolites and hormones including glucose, fructose, TG, FFA, ketones, insulin, and for the VLDL-lipoproteins, apolipoprotein B100, VLDL-TG concentration, and TG-palmitate lipogenesis. Once the samples have been processed for mass spectrometry and the data acquired, the processed samples will be kept until at least 10 years after publication (the stable isotope does not decay and the samples retain their value). DEXA is used to measure total and regional fat mass and fat-free mass, a FibroScan® ultrasound is performed to measure liver elastography (liver stiffness due to fibrosis), and MRI is used to assess liver fat. Indirect calorimetry is performed to measure energy expenditure, and skin oil collected (Sebutape®) to measure fatty acid composition. **Table 1** shows how the timeframe over which the 324 ml of blood is donated by the subject.

Table 1. Accounting of Blood Usage

Procedure	Volume of whole blood (mls)
Screening blood chemistries	40
V1. Baseline inpatient study	100
V2. D4 safety blood draw	10
V3. D6 safety blood draw	10
V4. D9 safety blood draw	14
V5. Follow-up inpatient study	140
V6. Follow-up safety blood draw	10

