Three days before visit 1, the subject is provided with food and beverages to meet his total energy needs for weight stability. No alcohol will be consumed during this time. The meals are made up of commercially available foods and the composition is based in foods the subject normally consumes.

Baseline Visit 1: Before arriving to the CRC, the subject will go to Fairview Digestive Health Clinic for a 15 minute FibroScan. If a FibroScan becomes available to be housed in the hospital, then this trip to Fairview would not be necessary and the measurement would be made during the inpatient study. The CRC will begin at 4:00 PM and take 24 hours and the subject will undergo several procedures. The first procedure is MRI to assess liver fat content. Next, after returning to the CRC, an IV line will be placed in one of the arms and an isotope ($^{13}\text{C}_1$ -acetate, 10g/1200 mL half-normal saline) will be infused through that IV. Afterward, the subject will be fed dinner and then undergo a skin test, where a piece of tape will be placed on the forehead for 30 minutes to collect oils produced by the skin. The subject will sleep overnight at the CRC. At 6:00 AM the next morning, the subject will undergo calorimetry and a second IV line will be placed in the other arm. This IV will be used to draw blood. Following this, he will be asked to consume a sugary drink to begin the oral sugar tolerance test (OSTT). The calorimetry test will be performed again at 9:30 AM and blood will be drawn intermittently until 2:00 PM. The total amount of blood drawn will be 100 mls. After the final blood draw, the subject will be fed lunch and then body composition will be measured by DEXA. After this, he can leave the CRC. If all

baseline procedures are successful, the subject will be given 10 days of drug to begin taking the first dose that evening. Each day, he will take a single pill with water before 10:30 PM (or at bedtime if before 10:30 PM). The study physician, [name], will oversee the prescribed dosage the subject will take. This dosage will be determined in consult with the Safety Officer, [name], according to the attached Dosing Decision Tree.

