The OSTT is a combination of glucose and fructose consumed in 180 ml of water. Specifically, over a period of 15 min, the subject will ingest a "Kool-Aid like" solution of 0.9g/kg fructose and 0.3g/k glucose in water. After the baseline test is completed, the subject takes home all food/beverages that he will consume until he returns for visit 2.

Safety Blood Draw Visits 2 and 3: As shown in **Figure 1**, the subject will return to the CRC for a single blood draw in the morning, 2 days following the baseline visit. The subject is instructed not to exercise on this morning before this blood draw. For 12 hours before these visits, he is asked to not eat or drink anything besides water. Blood will be taken (10 ml) and vitals will be checked. This visit will take about 30 minutes. On day 4 following the baseline visit, the subject will return for safety blood draw visit 3 and the procedures will be the same as safety blood draw visit 2. At the end of visit 3, the subject takes home food to eat until visit 4.

Safety Blood Draw Visit 4: The subject will return to the CRC for a third safety blood draw and all procedures done at the previous safety blood draws will be repeated, with the addition of the skin test. A small amount of blood will be drawn (14 mls). The subject is asked to not exercise on this morning before this blood draw. For 12 hours before he comes to the visit, the subject is told to not eat or drink anything besides water. The subject is told not to apply any lotion or skin products to the face on the morning of this visit. This visit will take about 45 minutes. At the end of visit 4, the subject takes food home to keep him weight stable until Follow-up visit 5.

Follow-Up Visit 5: On the day of the subject's last dose of medication, he will return to the CRC for the follow-up visit. This visit is exactly the same as the baseline visit, however, blood will also be drawn four times during the night to assess drug pharmacokinetics. The subject will come to the CRC at 4:00 PM and stay for 24 hours. The total blood draw will be 140 mls. Following this visit, the treatment portion of this study is over and the subject will discontinue taking the drug.

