The health history form and all subject screening and experimental data and pertinent medical paper records will be placed in individual files and coded for de-identification. This information will only be accessible to the principal investigator, co-investigator, or approved research personnel. All records will be kept in a locked filing cabinet, which only the research personnel have access to. Computerized records of experimental data will be similarly coded and will be maintained on a password secure system. The only confidential information to be disclosed would relate to the subject's medical history. The purpose of obtaining a careful medical history is to verify that the patient meets the inclusion/exclusion criteria. All medical and biographical information will be held in strict confidentiality and no disclosures of personal identity will be made unless specifically requested by the subject. Copies of signed consent forms, as well as the experimental log book, are kept in a locked file cabinet in the laboratory. Only subject ID numbers are used to also insure confidentiality. Participants will not be individually identified in any publications. The participants' right to privacy will be protected to the highest extent possible.

Protection of materials, and privacy

All sample tubes are coded to conceal the subjects' identities and no identifying information is present on the tubes. They are labeled with the subject's three-letter code identifier and the date. No tools (e.g., cell lines, probes, etc) will be generated from any of this material. The study will be conducted in accordance with Good Clinical Practice and HIPAA guidelines. Only the Investigators and study coordinator will have access to the codes. Aside from the sample sent to the Sponsor (3V Biosciences) the samples will not be shared with other investigators within the University of Missouri or outside the University. No identifying information will be shared or reported in any publication.

Potential benefits to human subjects and others

The research plan tests whether the drug will lower liver fat in men with risks for future nonalcoholic fatty liver disease. Development of such a drug would aid the millions of U.S. citizens who suffer from this condition. There is no direct benefit for the subjects and all study procedures are voluntary.

Reducing risk in participants

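### Masking to visit is stated only for the biochemical assays and should be extended to the before/after MRI liver-fat reading, a secondary or exploratory measure

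*Combined protocol and SAP*

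**What the plan says.** The overall design paragraph in the Background section is the only place that deals with blinding. It describes an uncontrolled before/after study: "The study design is a repeated-measures, with each subject serving as his own control". It then says "The study will be unblinded with respect to the research staff working directly with the subjects", and makes one exception: "laboratory personal who will be running the biochemical analyses will be blinded to whether they are analyzing baseline or post-treatment samples".

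MRI is a study measurement. Under Study Details, in the list of inpatient measurements, "MRI is used to assess liver fat". In the Schedule of Events, Baseline Visit 1, "The first procedure is MRI to assess liver fat content". Follow-Up Visit 5 repeats it by reference: "This visit is exactly the same as the baseline visit".

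On the role of liver fat, the section on potential benefits says "The research plan tests whether the drug will lower liver fat in men with risks for future nonalcoholic fatty liver disease". The numbered aims say something narrower. Hypothesis 3, for example, is that "the last six subjects will demonstrate a significant reduction in fasting and stimulated lipogenesis", and liver fat appears in none of the three hypotheses.

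A radiologist is listed among the participating staff, with no stated task.

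**The concern.** Masking the assay staff shows that the plan accepts the principle: whoever produces a before/after measurement should not know which value is after treatment. The sentence covers samples and biochemical analyses, and an MRI scan is neither. Liver fat is therefore left out, although it is paired across the same two visits and is described in one place as something the plan tests.

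Every man's second scan is a treated scan, so a reader who knows the visit knows the treatment status. If quantification involves choices such as where a region is placed, expectation could push post-treatment values down. A bias in a common direction does not average out over subjects. The stated future use of the drug is in fatty liver disease, so a fall in liver fat reported from this pilot would naturally be taken as evidence of effect.

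**Working it through.** The plan gives no figure to reproduce on this point, so the check is first a reading of the text and then an illustration on assumed values.

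**1. Does the blinding sentence reach MRI?**
- Who is masked: laboratory staff running biochemical analyses (Background, overall design).
- What they are masked to: whether a sample is from baseline or post-treatment.
- MRI liver fat: an image measurement, not a sample and not a biochemical analysis.
- Any other masking statement for images: none in the Schedule of Events, Study Details or the statistical section.

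The sentence does not reach MRI. Nor does the text say that the reader is unmasked. The unblinded group is staff who work directly with subjects, and whether that includes whoever quantifies the scans is not stated.

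**2. Is liver fat a before/after comparison?** Yes. MRI is the first procedure at visit 1, and visit 5 repeats the baseline visit. With 12 men this gives 12 × 2 = 24 scans.

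**3. Would later, masked reading hold anything up?**
- Eligibility: liver fat is in neither the inclusion nor the exclusion list.
- Dose decision: the inputs named in the Summary of study objectives are side effects, reduction in lipogenesis and PK. The decision-tree figure is not available in the text, so this rests on the named inputs.
- Sample size: built on lipogenesis only.

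No decision described in the text waits for a liver-fat value.

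**4. What could a shift do?** The documents give no liver-fat mean, SD or reader error, so the following shows sensitivity only. Suppose that the drug has no effect on liver fat, but that reading moves the mean paired difference by *b* standard deviations of the differences. The statistical section names a paired t-test without assigning it to liver fat; assume that it is used, two-sided at 5%. The test statistic is then noncentral t with n − 1 degrees of freedom and noncentrality b√n. The rejection rate is the probability of falling beyond ±t(0.975, n − 1).

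| Assumed b | b√12 | Rejection, n = 12 | b√6 | Rejection, n = 6 |
|---|---|---|---|---|
| 0 | 0 | 5.0% | 0 | 5.0% |
| 0.10 | 0.346 | 6.2% | 0.245 | 5.5% |
| 0.25 | 0.866 | 12.4% | 0.612 | 8.0% |
| 0.50 | 1.732 | 35.3% | 1.225 | 17.1% |

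The n = 12 column pools all subjects; n = 6 corresponds to Parts 1 and 2 together or to Part 3 alone. For a given b the rate rises with n, because more subjects shrink the standard error and leave the shift where it is. At b = 0.10 the effect is slight, and at b = 0.50 it is serious. The documents do not show where in this range, or outside it, the trial would lie.

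**The case against.** The strongest reply is that liver fat is not an endpoint to which the plan commits. The Purpose section concerns liver fat synthesis. The aims, hypotheses and sample size concern lipogenesis, which is measured by mass spectrometry and falls under the stated blinding. MRI is listed beside DEXA, FibroScan, calorimetry and skin-oil collection. The one sentence that says liver fat is tested stands in the benefits section and may be loose wording for fat synthesis. This stands: it limits the point to a secondary or exploratory measure in a 12-man pilot.

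A second reply is that the text describes no unmasked reading. A reader might infer from the open design and the listed radiologist that the scans are read with the visit visible and with regions placed by hand. The documents do not support that. They are silent on reader, method and masking, and automated quantification would leave little room for expectation. This also stands.

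Third, masking is not the only safeguard. A fixed region template, automated quantification or duplicate reading would also limit reader effects. Nor would masking address other before/after threats, such as the supplied diet or regression to the mean.

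What remains is that the plan masks one class of before/after measurement and leaves out another that can be masked at little cost.

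**Conclusion.** The point holds as a cheap improvement. As written, masking to visit covers the biochemical assays only, and the paired MRI liver-fat comparison has no stated protection against reader expectation. This affects how far a liver-fat change from this study could be relied on. It does not touch the lipogenesis results, the sample size or the dose-decision inputs named in the text.

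The size of any bias cannot be derived from the documents. A reader might be tempted to assume liver fat of about 10% and reader differences of 0.5 to 1.0 point, and so conclude that a null drug would show a relative fall of 5% to 10% (0.5/10 and 1.0/10). That would be an assumed bias divided by an assumed mean. No eligibility criterion sets a liver-fat level, diagnosed liver disease is excluded, and variability between readings is not the same as a shift in one direction. The rejection rates in the working carry the same caution: they are conditional on an assumed shift and are not estimates for this trial.

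**What to change.** Extend the blinding sentence in the overall design paragraph along these lines:

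> MRI liver fat will be quantified on scans stripped of date and visit, each given a random code, and read in random order in one batch after all subjects have finished (at the least, after each man's visit 5). Any prompt look at a scan for incidental findings will involve no liver-fat quantification. FibroScan is not blinded.

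Stating whether quantification is automated or uses hand-placed regions would also let readers judge the remaining risk. FibroScan needs its own sentence because the measurement is made with the subject present, so recoding afterwards cannot mask it.

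The cost is the recoding of 24 scans by someone other than the reader, and liver-fat values that arrive later. No extra subject, visit or scan is needed. If the same radiologist does the prompt look and the later reading, some recall is possible with so few scans. Batch reading after the last subject reduces this, and a different person for one of the two tasks would remove it, at the price of a second reader.

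### The laboratory is meant to be blind to visit, but the only written labelling rule puts subject code and date on every tube, so a subject's two inpatient dates show which samples are post-treatment.

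*Combined protocol and SAP*

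**What the plan says.** Four parts of the protocol bear on this.

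- **Background (overall design).** The study is a within-subject comparison of baseline with follow-up, open to the staff who deal with the subjects. Laboratory staff running the biochemical analyses "will be blinded to whether they are analyzing baseline or post-treatment samples".
- **Protection of materials, and privacy.** The rule applies to all sample tubes, and its stated aim is to hide who the subject is: "They are labeled with the subject's three-letter code identifier and the date". It adds: "Only the Investigators and study coordinator will have access to the codes".
- **Baseline Visit 1.** Once the baseline procedures are complete, "the subject will be given 10 days of drug to begin taking the first dose that evening". On blood volume: "The total amount of blood drawn will be 100 mls".
- **Follow-Up Visit 5.** "On the day of the subject's last dose of medication, he will return to the CRC for the follow-up visit". At this visit "blood will also be drawn four times during the night to assess drug pharmacokinetics", and "The total blood draw will be 140 mls".

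No section describes a date-free sample number, relabelling before assay, or a random run order.

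**The concern.** The blinding statement and the labelling rule do not fit together. The rule protects identity. It does nothing to hide the visit, because it prints the one item, the date, that puts a subject's two sample sets in order.

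There is no control arm and no randomisation, and the clinical staff know which visit is which. Masking of the assay staff is therefore the only protection of this kind in the plan. The assay results also have an early use: under Summary of study objectives, the effect on lipogenesis in the first 6 subjects helps decide the dose for the last 6. The blind should work from the first subject onward.

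**Working it through.** The plan gives no figure to reproduce. The check sets its statements side by side and counts days.

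**1. Does the order of dates identify the visit?** Take the day of the baseline sugar test as day 0.

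- The first dose is that evening, day 0 (Baseline Visit 1).
- Ten doses on consecutive evenings fall on days 0 to 9.
- Visit 5 begins on the day of the last dose, day 9, and its sugar test is the next morning, day 10 (Follow-Up Visit 5).
- Gap between corresponding samples: 10 − 0 = 10 days, assuming no missed or delayed dose.

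A missed or delayed dose could change the gap but not the order. Under any one code, the earlier inpatient date is baseline and the later is post-treatment.

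**2. Is the code key needed?** No. The key links a code to a person. Code and date are both printed on the tube, so two tubes with the same code can be ordered without knowing whose they are. Restricting the key does not protect the visit blind.

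**3. How many samples are affected?** 12 subjects × 2 inpatient visits = 24 sample sets, or 12 pairs. If the analyst sees both dates for each code, 12 of 12 pairs can be ordered. From one label alone, with no knowledge of the subject's schedule, none can.

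**4. Is there a second cue?** Visit 5 has 4 overnight pharmacokinetic draws that baseline lacks, and 140 − 100 = 40 mL more blood. An analyst handling aliquots would not necessarily see the total volume, and the plan does not say whether the pharmacokinetic tubes reach the same analysts. This cue is only possible, and the conclusion does not depend on it.

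**5. Does anything else restore the blind?** Reducing risk in participants says that test results follow the laboratory's internal controls, but not that these controls hide the visit.

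**The case against.** The strongest reply is that this is silence, not contradiction. The labelling sentence sits in a privacy section and does not describe assay workflow. Study Details shows that assays are run on derived material (plasma, lipoproteins, samples processed for mass spectrometry), and the laboratory may re-code at that stage. That possibility stands, so actual unblinding is not shown. But the rule is written for all sample tubes and no other rule exists, so the plan as written does not show how it keeps its own commitment.

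Second, the mechanism is conditional. An analyst must see both dates under one code, and "They are labeled with the subject's three-letter code identifier and the date" has to mean the collection date, which is the natural reading but not spelled out. The plan says nothing about batching or how samples are assigned to analysts. This stands: 12 of 12 is the worst case.

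Third, the pharmacokinetic cue is weak. The privacy section mentions a sample sent to the sponsor without saying which, so those tubes may never reach the assay staff. This also stands, and the cue carries little weight.

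Fourth, no consequence is demonstrated. The measure is instrumental, no subjective scoring of it is described, no specific route to a biased result is visible, and the Sample size section calls the study a pilot. This limits the importance of the point but does not remove it.

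Fifth, the only effect that can be calculated counts against relabelling, since code and date help guard against swapped samples. That cost is real and is quantified with the fix.

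**Conclusion.** The point holds, as a low-priority improvement. Followed as written, the labelling rule can defeat the only blinding the protocol describes: an analyst who sees both inpatient dates for each code can order all 12 pairs.

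This assumes that the date on the label is the collection date, that the same analyst sees both visits' tubes for a subject, and that no unwritten re-coding takes place. The 10-day gap further assumes that no dose is missed or delayed, but the order of the dates does not need that assumption.

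The size of any bias cannot be derived from the documents and is probably limited for a mass-spectrometry measure, so no figure for bias or false-positive risk is attached. The conclusion does not depend on the significance level, the SD or the assumed effect.

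**What to change.** Amend the labelling rule under Protection of materials, and privacy:

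- Aliquots sent for biochemical and mass-spectrometry analysis carry only a random sample number, with no subject code, date or visit.
- The study coordinator holds the key, provided the coordinator does not run the assays.
- A subject's results are final before his samples are unmasked. Unmasking can go subject by subject, so results remain available for the planned dose review after the first 6.
- If the same analysts handle the Visit 5 pharmacokinetic tubes, those are coded so that they do not reveal the visit.
- If the laboratory already re-codes aliquots, stating that procedure is enough.

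Running a subject's two visits in one batch in random order is optional.

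**Cost.** One amended sentence, a key file kept by existing staff, modest relabelling work and a small risk of mislabelling. That risk matters in a paired study this small. If every subject had the 2-point fall used in the Sample size section, one swapped pair would give a mean of (11 × 2 − 2)/12 = 20/12 = 1.67 points instead of 2.0, a loss of 0.33/2.0, or about 17%. A check of each relabelled aliquot against the key reduces the risk but does not remove it.
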